Objectives:	
Primary Objectives The primary objectives of this study are to:
 
 • Determine the safety and tolerability of CPX-351 (cytarabine:daunorubicin liposome complex) with quizartinib in patients with relapsed or refractory fms-like tyrosine kinase 3 (FLT3)-internal tandem duplication (ITD) mutation-positive acute myeloid leukemia (AML). • Determine the overall complete morphologic (per World Health Organization) and molecular remission rate of CPX-351 and quizartinib in patients with relapsed or refractory FLT3-ITD mutation-positive AML. 
Secondary Objectives The secondary objectives of this study are to:
 
 • Define the time to absolute neutrophil count and platelet count recovery • Define the number of patients proceeding to an allogeneic stem cell transplant (alloHCT) • Determine time to disease progression or duration of response • Determine event-free survival • Determine overall survival • Define the percentage of patients who develop late responses • Define the number of patients who can receive consolidation and maintenance therapy on this study • Define the treatment-related mortality rate of this combination • Determine the percentage of patients who achieve a PR or molecular complete remission (CR) • Determine the mean elapsed time for patients to achieve molecular CR • Determine whether quizartinib is tolerable after alloHCT or donor lymphocyte infusion. 	
Study Design:	This is a multi-center, non-randomized, open-label, two-part prospective Phase II clinical trial in patients with relapsed or refractory FLT3-ITD mutation-positive AML. The study is designed to assess the safety and tolerability as well as the efficacy of administering CPX-351 (cytarabine:daunorubicin liposome complex) with quizartinib, a second-generation FLT3 inhibitor. The plan for administration is divided into three phases: induction, consolidation, and maintenance. Approximately 34 patients are planned to be screened and enrolled.	

CONFIDENTIAL

STUDY DRUG: QUIZARTINIB
PROTOCOL DATE: 10 AUGUST 2020

DEVELOPMENT INNOVATIONS STUDY NUMBER: AML 48
VERSION 4.0

	
A total of 10 patients will be enrolled in the safety lead-in, which is designated as Part 1 of the study. If ≥ 8 patients meet the pre-specified safety parameters, an additional 24 patients will be enrolled in Part 2 of the study. All patients will be assessed for response.

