5. STUDY DESIGN

This is a multi-center, non-randomized, open-label, two-part prospective Phase II clinical trial in patients with relapsed or refractory FLT3-ITD mutation-positive AML. The study is designed to assess the safety and tolerability as well as the efficacy of administering CPX-351 (cytarabine:daunorubicin liposome complex) with quizartinib, a second-generation FLT3 inhibitor. The plan for administration is divided into three phases: induction, consolidation, and maintenance. Approximately 34 patients are planned to be screened and enrolled. Patient participation is expected to be 4 years.

A total of 10 patients will be enrolled in the safety lead-in. The safety lead-in portion of the study is designated as Part 1. If >3 patients experience delayed neutrophil count recovery >56 days from the first day on the study regimen, or delayed thrombocytopenia recovery >56 days from the first day on the study regimen, or if >3 patients develop a non-hematologic toxicity, defined as a Grade 4 non-hematologic adverse event determined to be probably related to the combined treatment, or a Grade 4 neutropenia, then the study will be terminated.

Assuming safety parameters are met, the first 10 patients will be followed for response in the Part 2 of the study. An additional 24 patients will be enrolled in Part 2 of the study (induction, consolidation and maintenance). All patients will be assessed for response.

Patients who fail to respond to therapy will be followed until a new therapy is instituted. . Patients who experience an AE that results in the discontinuation of study treatment will be

[figure not shown]
CONFIDENTIAL

STUDY DRUG: QUIZARTINIB
PROTOCOL DATE: 10 AUGUST 2020

DEVELOPMENT INNOVATIONS STUDY NUMBER: AML 48
VERSION 4.0

followed until resolution/stabilization for AEs attributed to the medication. Outcomes for all patients will be assessed for 24 months from the date of last treatment.

Figure 1 Study Schema

*All treatment phases follow a 28-day cycle. Induction and re-induction consist of: CPX-351 (liposomal daunorubicin 44 mg/m² IV and cytarabine 100 mg/m² IV) + quizartinib 30 mg PO QD. The maintenance phase: begin quizartinib 30 mg PO QD on Days 1-14. If there are no toxicities and QTcF is maintained ≤ 450 msec, increase dose to 60 mg QD on Day 15.

[†]For one cycle

[‡]For up to two cycles

CONFIDENTIAL

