7.5.2 Precautions and Risks Associated with CPX-351

- Cardiotoxicity

The total cumulative dose of non-liposomal daunorubicin >550 mg/m² has been associated with an increased incidence of drug-induced congestive heart failure. In patients who received radiation therapy, the maximum tolerable lifetime dose is 400 mg/m². Calculate maximum lifetime exposure prior to each cycle as shown in Table 1.

Table 1 Cumulative Exposure of Daunorubicin per Cycle of CPX-351

Therapy	Daunorubicin per Dose	Number of Doses per Cycle	Daunorubicin per Cycle
First induction cycle	44 mg/m ²	3	132 mg/m ²
Second induction cycle	44 mg/m ²	2	88 mg/m ²
Each consolidation cycle	29 mg/m ²	2	58 mg/m ²

CONFIDENTIAL

See dose modification/administration guidelines (Appendix G).

- Hemorrhage

12% Grade ≥ 3 (8% in control/7+3 arm), fatal non-disease associated CNS hemorrhage 2% (0.7% in control arm)

- Hypersensitivity

Known in patients receiving cytarabine and daunorubicin. See dose modification/administration guidelines (Appendix G).

- Tissue necrosis

Administer by central venous catheter

- Embryo-fetal toxicity

Counsel to avoid pregnancy, and to use contraception through 6 months after last administration of agent. Because of the potential for serious adverse reactions in breastfed infants, advise lactating women not to breastfeed during treatment with CPX-351. In males, CPX-351 may cause infertility. In male patients wishing to conceive in the future, cryopreservation of sperm prior to administration is recommended.

- Cytopenias

Prolonged thrombocytopenia (<50 beyond Day 42) 28% (versus 12%) in induction and 25% (versus 16%) in consolidation; prolonged neutropenia (ANC <500 beyond Day 42) 17% (versus 3%) in induction and 10% (versus 3%) in consolidation. See dose modification/administration guidelines (Appendix G).

- Chemistry abnormalities

Hyponatremia (14%, 6% with consolidation), hypokalemia (9%, 6% with consolidation), hypoalbuminemia (7%, 2% with consolidation), hyperbilirubinemia (6%, 2% with consolidation), and elevated ALT (5%, 0% with consolidation); all were similar in comparison to 7+3.

The most common serious adverse reactions (incidence $\geq 5\%$) were dyspnea, myocardial toxicity, sepsis, pneumonia, febrile neutropenia, bacteremia and hemorrhage. Adverse reactions led to discontinuation of CPX-351 in 18% of patients (13% in the control arm).

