10. STATISTICAL CONSIDERATIONS

10.1 Statistical Design

This is a multi-center, open-label, two-part prospective Phase II study of patients with relapsed or refractory FLT3-ITD mutation-positive AML. The study is designed to assess the safety and tolerability as well as the efficacy of administering CPX-351 with quizartinib, a second-generation FLT3 inhibitor.

A response rate (CR + CRi) of $\geq 50\%$ is targeted with 40% or less considered unacceptable. This is assumed to be an acceptable estimate based on CR + CRi/CRp of 48.2% reported with quizartinib monotherapy in a relapsed or refractory patient with FLT3-ITD AML (Cortes et al 2019). Of note, prior FLT3-targeting inhibitor exposure is permitted on this study. However, patients receiving a prior FLT3-targeting inhibitor were excluded in the QUANTUM-R study. Expected CR+CRi in relapsed or refractory patients receiving standard intensive or non-intensive salvage chemotherapy harboring an FLT3 mutation is 27% (Cortes et al 2019). The estimated response in those with relapsed/refractory FLT3-ITD AML receiving CPX-351 alone cannot be estimated. However, in a poor-risk EPI patient population, CR+CRi was reported as 39.3% (Cortes et al 2015). However, FLT3-ITD mutation presence was not utilized in the generation of EPI prognostication, and those with an FLT3-ITD mutation could in fact have a reduced response within all EPI risk groups. Thus, the expected response must be based upon the QUANTUM-R study of those receiving standard salvage options harboring an FLT3-ITD mutation.

In the safety lead-in, 10 patients will be enrolled to receive CPX-351 with quizartinib. If > 3 patients experience delayed neutrophil count recovery > 56 days or delayed thrombocytopenia recovery > 56 days from the first day on the study regimen, or if > 3 patients develop a non-hematologic toxicity, defined as a Grade 4 non-hematologic AE determined to be probably related to the combined treatment or a Grade 4 neutropenia, then the study will be terminated.

Assuming safety parameters are met, the first 10 patients will be followed for response in Part 2 of the study.

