10.5 Analysis Time Points

10.5.1 Safety Review

The safety lead-in consists of the first 10 patients enrolled. If >3 patients experience delayed neutrophil count recovery >56 days from the first day receiving the study regimen, defined as having a peripheral blood ANC <500/ μ L without evidence of residual disease by BM biopsy, or if >3 patients develop a non-hematologic toxicity, defined as a Grade 4 non-hematologic AE determined to be probably related to the combined treatment, then the study will be terminated.

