10.5.2 Final Analysis

The final analysis of the study will occur following the last visit of the last patient.

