11.1.6 Assessment of Adverse Events

All AEs and SAEs whether volunteered by the patient, discovered by study personnel during questioning, or detected through physical examination, laboratory test, or other means will be reported appropriately. Each reported AE or SAE will be described by its duration (e.g., start

CONFIDENTIAL

STUDY DRUG: QUIZARTINIB
PROTOCOL DATE: 10 AUGUST 2020

DEVELOPMENT INNOVATIONS STUDY NUMBER: AML 48
VERSION 4.0

and end dates), regulatory seriousness criteria if applicable, suspected relationship to the study drug (see following guidance), and actions taken.

To ensure consistency of AE and SAE causality assessments, Investigators should apply the following general guideline:

YES: There is a plausible temporal relationship between the onset of the AE and administration of the study medication, and the AE cannot be readily explained by the patient's clinical state, intercurrent illness, or concomitant therapies, and/or the AE follows a known pattern of response to the study drug, and/or the AE abates or resolves upon discontinuation of the study drug or dose reduction and, if applicable, reappears upon re-challenge.

NO: Evidence exists that the AE has an etiology other than the study drug (e.g., pre-existing medical condition, underlying disease, intercurrent illness, or concomitant medication), and/or the AE has no plausible temporal relationship to study drug administration (e.g., cancer diagnosed 2 days after first dose of study drug).

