11.4.1.1 **QTc Prolongation, TdP and Other Ventricular Arrhythmias**

Subjects who experience >480 msec QTcF prolongation and undergo dose interruption and/or reduction must be monitored closely with ECGs, performed twice weekly for the first week of the QTcF prolongation and then weekly thereafter until the QTcF prolongation is resolved, as described in Section 8.2.1. A Grade ≥ 3 QTcF prolongation either serious or non-serious and whether or not causally related, must be recorded as AE or SAE in the Electronic Data Capture (EDC) system within 24 hours of awareness of the central ECG laboratory reading, with the Investigator's assessment of seriousness, causality, and a detailed narrative.

11.4.1.2 **Combined Elevations of Aminotransferases and Bilirubin**

Combined elevations of aminotransferases and bilirubin, either serious or non-serious and whether or not causally related, meeting the laboratory criteria of a potential Hy's Law case [ALT or AST ≥ 3 x ULN with simultaneous total bilirubin ≥ 2 x ULN] should always be recorded as an AE or SAE within 24 hours of awareness, with the Investigator's assessment of

CONFIDENTIAL

seriousness, causality, and a detailed narrative. Patients will be monitored as described in Appendix F.

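### Numeric study-level toxicity rules end at the 10-patient lead-in and are worded inconsistently; no number prompts a cumulative safety review for the 24 Part 2 patients

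*Combined protocol and SAP*

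**What the plan says.** Section 10.5.1 sets the safety review: "The safety lead-in consists of the first 10 patients enrolled". It terminates the study if more than 3 patients have neutrophil recovery delayed beyond 56 days without residual disease on marrow biopsy, or if more than 3 have a Grade 4 non-hematologic event judged probably related to the combination.

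Three other places give a wider rule: the synopsis (Statistical Methodology), Section 5 and Section 10.1. They add delayed platelet recovery, and they extend the Grade 4 limb to events "determined to be probably related to the combined treatment or a Grade 4 neutropenia, then the study will be terminated". The synopsis Study Design row gives a third version: if at least 8 "patients meet the pre-specified safety parameters, an additional 24 patients will be enrolled in Part 2 of the study".

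After the lead-in, Section 5 says: "An additional 24 patients will be enrolled in Part 2 of the study (induction, consolidation and maintenance"). The only later time point in Section 10.5 is in 10.5.2: "The final analysis of the study will occur following the last visit of the last patient".

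Part 2 does keep other safeguards:
- dose and discontinuation rules for the individual patient (Section 8, Appendices F and G), and no consolidation after 56 days of cytopenia (Section 5.2.2);
- 24-hour SAE reporting (Section 11.2);
- reporting of events of special interest: for example, Section 11.4.1.1 says Grade 3 or worse QTcF prolongation "must be recorded as AE or SAE in the Electronic Data Capture (EDC) system within 24 hours of awareness";
- SUSAR submission within 7 or 15 days (Section 11.5.1);
- continuing IRB review and company safety updates (Section 13.1);
- termination by the sponsor or IRB (Section 3.3).

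**The concern.** Safety and tolerability of this combination is the first-listed primary objective, and Section 1.5 names prolonged neutropenia and thrombocytopenia as the effect most to be expected. Yet 24 of the 34 patients are treated after the last numeric check. The continuing safeguards work patient by patient or event by event, and SUSAR reporting covers only unexpected events, so an excess of an expected toxicity such as prolonged cytopenia need not surface that way. Whether anyone looks at the accumulated count is left to discretion.

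The rule that would be carried forward is itself unsettled. The sections can give opposite answers on the same 10 patients. The Grade 4 limb has no closing date. It counts probable relation, while Section 11.1.6 gives investigators only YES or NO, with YES beginning "There is a plausible temporal relationship between the onset of the AE and administration of the study medication".

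**Working it through.** **1. The plan's own figure.** No error rate is given for the safety rule. The stated efficacy design reproduces by exact binomial: P(X ≥ 13 | n = 30, 0.27) = 0.039 and P(X ≥ 13 | n = 30, 0.50) = 0.819, against a 0.05 target and 80% power. The same method is used below.

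**2. The lead-in versions side by side.**

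| Source | Part 2 does not open if | Platelet recovery | Grade 4 neutropenia | Residual-disease condition |
|---|---|---|---|---|
| Synopsis, Study Design | 3 or more of 10 fail | not stated | not stated | not stated |
| Synopsis statistics; Sections 5, 10.1 | more than 3 on a limb | yes | yes | no |
| Section 10.5.1 | more than 3 on a limb | no | no | yes |

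Three patients with delayed neutrophil recovery and no other event fail the first version and pass the third. Under the third, up to 3 + 3 = 6 different patients could be affected and the study would continue.

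**3. What the 10-patient gate does.** No unacceptable toxicity rate is stated, so the rates p are assumptions. The nearest figures in the documents are for CPX-351 (Section 7.5.2): "prolonged neutropenia (ANC <500 beyond Day 42) 17% (versus 3%) in induction and 10% (versus 3%) in consolidation", and 28% prolonged thrombocytopenia in induction. Both use Day 42, not Day 56. For one limb, P(stop) = P(X ≥ 4 | n = 10, p). At p = 0.30 this is 0.350, so the gate passes with probability 0.650; Part 2 would then expect 24 × 0.30 = 7.2 further events. Under the synopsis design row, P(X ≥ 3 | n = 10) is 0.322 at 20% and 0.617 at 30%, against 0.121 and 0.350 for more than 3, so the choice of version matters.

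**4. Grade 4 neutropenia.** If it counts toward the more-than-3 total and its rate is an assumed 60%, P(X ≥ 4 | n = 10, 0.60) = 0.945. The wording would then very likely terminate the study.

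**5. A pause look at 20 patients.** The trigger is 8 of 20, the same 40% proportion as 4 of 10. Probability added = sum over x = 0 to 3 of P(x of the first 10) × P(at least 8 − x of the next 10). At p = 0.30:

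0.0282 × 0.0016 + 0.1211 × 0.0106 + 0.2335 × 0.0473 + 0.2668 × 0.1503 = 0.053.

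Patients spared = (34 − 20) × added with immediate readout, or (34 − 24) × added if 4 more enrol while the tally is made.

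| p | Gate alone | Added | Total | Spared, immediate | Spared, 4-patient lag |
|---|---|---|---|---|---|
| 0.17 | 0.074 | 0.004 | 0.078 | 0.05 | 0.04 |
| 0.20 | 0.121 | 0.009 | 0.130 | 0.12 | 0.09 |
| 0.28 | 0.298 | 0.041 | 0.339 | 0.57 | 0.41 |
| 0.30 | 0.350 | 0.053 | 0.403 | 0.73 | 0.52 |
| 0.40 | 0.618 | 0.101 | 0.719 | 1.42 | 1.01 |
| 0.50 | 0.828 | 0.091 | 0.919 | 1.28 | 0.91 |

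Among trials that pass the gate, the look catches 0.053/0.650 = 8% at p = 0.30, 0.101/0.382 = 26% at 0.40 and 0.091/0.172 = 53% at 0.50.

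**6. Fewer patients at risk on the haematologic limb.** Patients with residual disease cannot count. If half are at risk (an assumption, matching the 50% target response rate), a 30% or 40% rate among them is 15% or 20% overall. The look then adds 0.002 or 0.009 and spares about 0.02 or 0.12 patients.

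**The case against.** The strongest reply is that Part 2 is already watched and a number buys little. The trial is open-label and single-arm, sponsor safety staff receive every SAE within 24 hours, and the sponsor or IRB can stop at any time. At 17% and 28% the extra look adds only 0.4 and 4.1 percentage points. At 28%, a pause might reflect nothing more than the known cytopenia of CPX-351. At 30%, about 60% of trials would still run to completion. All of this stands. It limits the size of the point, but it does not supply a number that prompts a cumulative look, and it does not touch the conflict between versions of the lead-in rule.

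A reader might infer that Part 2 patients are unmonitored. The documents do not support that: the safeguards listed above continue and can lead to a stop.

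A reader might also take the limit of more than 3 in Section 10.5.1 to run over all 34 patients, since that sentence does not repeat the denominator. The sentence before it, and Sections 5 and 10.1, place it in the lead-in. Over 34 patients it would stop a regimen with 4/34, or about 12%, toxicity.

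**Conclusion.** Two things hold. Every numeric study-level toxicity rule is confined to the first 10 patients. The lead-in rule also exists in conflicting forms, one of which, read literally, would very likely end the study. The second is a decision-rule error; the first is a design choice that can be improved cheaply.

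The benefit of a 20-patient look should not be oversold. Per limb it adds about 5, 10 and 9 percentage points at 30%, 40% and 50%, and spares at most about 0.7, 1.4 and 1.3 patients per trial. The existing gate does most of the work, and the gain is smaller on the haematologic limb. These figures assume independent patients, a constant event rate, all 20 patients at risk and a prompt readout. The toxicity rates are assumptions because the documents state no unacceptable rate. For the same reason, nothing here shows that the regimen is too toxic.

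**What to change.** 1. **Use one lead-in rule in every section.** Stop if more than 3 of 10 meet limb (a), or more than 3 of 10 meet limb (b). Limb (a) is neutrophil or platelet recovery delayed beyond 56 days without residual disease. Limb (b) is a Grade 4 non-hematologic event with a causality answer of YES under Section 11.1.6. Delete the Grade 4 neutropenia wording and align the synopsis Study Design sentence.

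2. **Carry the same definitions forward in Section 10.5.1 to all treated patients.** Pause enrolment for sponsor safety review, without automatic termination, if 8 or more of the first 20 meet limb (a), or 8 or more of the first 20 meet limb (b). The limbs are counted separately.

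3. **Count limb (b) at any time on treatment up to the stated data cut for the look.** A 56-day window would lose most 60 mg maintenance exposure and most dosing after transplant. That matters because QTcF prolongation is dose-dependent: Section 7.5.1 gives 11% at 30 mg and 17% at 60 mg for Grade 2 or worse.

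4. **Report treatment-related deaths at the same look**, and print the operating characteristics with a statement that the gain is modest.

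The cost is one paragraph, matching edits to the synopsis and Sections 5 and 10.1, and one tally by existing sponsor safety staff. No committee, procedure or patient is added. The downside is a possible short pause, including for known CPX-351 cytopenia: per limb, total stop-or-pause probability goes from 0.121 to 0.130 at 20% and from 0.298 to 0.339 at 28%.

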2.2 Secondary Objectives

The secondary objectives of this study are to:

- Define the time to ANC and platelet count recovery
- Define the number of patients proceeding to an alloHCT
- Determine time to progressive disease (PD) or DOR
- Determine event-free survival (EFS)
- Determine OS
- Define the percentage of patients who develop late responses
- Define the number of patients who can receive consolidation and maintenance therapy on this study
- Define the treatment-related mortality rate of this combination
- Determine the percentage of patients who achieve a PR or molecular CR
- Determine the mean elapsed time for patients to achieve molecular CR
- Determine whether quizartinib is tolerable after alloHCT or DLI

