11.1.5 Recording and Reporting of Adverse Events

11.1.5.1 Recording of Adverse Events

All AEs will be recorded in the eCRF for all patients during the course of the research study, and the Investigator will give his or her opinion as to the relationship of the AE to the study treatment (e.g., whether the event is related or unrelated to study drug administration).

A description of the event, including its date of onset and resolution, whether it constitutes an SAE or not, any action taken (e.g., changes to study treatment), and outcome should be provided along with the Investigator's assessment of causality (e.g., the relationship to the study treatment). For an AE to be a suspected TEAE, there should be at least a reasonable possibility of a causal relationship between the protocol treatment and the AE. Adverse events will be graded according to the NCI CTCAE Version 5.0, and changes will be documented.

If the AE is serious, it should be reported immediately to the Development Innovations Safety Department. Other untoward events occurring in the framework of a clinical study are to be recorded as AEs (e.g., AEs that occur prior to assignment of study treatment that are related to a protocol-mandated intervention, including invasive procedures such as biopsies, medication washout, or no treatment run-in).

Any clinically significant signs and symptoms, abnormal test findings, changes in physical examination, hypersensitivity, and other measurements that occur will be reported as AEs and collected on the relevant eCRF screen.

Test findings will be reported as an AE if: the test result requires an adjustment in the study drug(s) or discontinuation of treatment; and/or test findings require additional testing or surgical intervention; a test result or finding is associated with accompanying symptoms; or a test result is considered to be an AE by the Investigator.

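### The lead-in toxicity event is limited to Grade 4, so a related event that is fatal without first being recorded as Grade 4 is not counted as toxicity; its causality term also needs matching to the recorded scale

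*Combined protocol and SAP*

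**What the plan says.** Section 10.5.1 fixes the group to be reviewed: "The safety lead-in consists of the first 10 patients enrolled". It ends the study on either of two counts, each set at more than three patients. The first limb is delayed neutrophil recovery: ANC below 500/µL more than 56 days after the first day of the regimen, with no residual disease on marrow biopsy. The second limb is non-hematologic toxicity, "defined as a Grade 4 non-hematologic AE determined to be probably related to the combined treatment, then the study will be terminated".

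Section 5 describes the toxicity in the same terms, "defined as a Grade 4 non-hematologic adverse event determined to be probably related to the combined treatment", and the synopsis matches it. Section 10.1 reads "defined as a Grade 4 non-hematologic AE determined to be probably related to the combined treatment or a Grade 4 neutropenia". The synopsis and Sections 5 and 10.1 thus add Grade 4 neutropenia, and also delayed platelet recovery; 10.5.1 has neither.

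Adverse events are graded by CTCAE version 5.0 (Section 10.4.3). On causality, Section 11.1.6 says "To ensure consistency of AE and SAE causality assessments, Investigators should apply the following general guideline" and then defines two answers, YES and NO. Section 11.1.5.1 asks for the investigator's opinion on relationship, "e.g., whether the event is related or unrelated to study drug administration". Deaths not attributed solely to progression go to SAE reporting (Section 11.3.4). One secondary objective is "Define the treatment-related mortality rate of this combination", with no stopping threshold attached.

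**The concern.** The lead-in is the only prespecified safety review before 24 more patients are enrolled, and safety and tolerability is the first-listed primary objective. Its toxicity count names one grade. A death from toxicity, the worst outcome, is not named in any of the four statements.

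Fatal toxicity is foreseeable from the protocol itself. Section 7.5.2 reports 2% fatal CNS hemorrhage with CPX-351, and Section 7.5.1 says that infection or hemorrhage under quizartinib can be fatal.

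A second, smaller problem is that the event must be rated *probably related* to the combined treatment, a category that the protocol's causality guideline does not contain. Two people scoring the same ten patients could reach different counts.

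**Working it through.** **Step 1: does any limb count a fatal event?**

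| Text | Non-hematologic event | Other limbs | Death mentioned? |
|---|---|---|---|
| Section 10.5.1 | Grade 4, probably related | Neutrophil recovery beyond 56 days | No |
| Synopsis, Sections 5 and 10.1 | Grade 4, probably related | Neutrophil or platelet recovery beyond 56 days; Grade 4 neutropenia | No |

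Grade 4 does not read as shorthand for Grade 4 and above, because the protocol writes Grade ≥3 where it means a floor (Sections 5.2.2, 5.2.4, 8.3.1 and 11.4.1.1). A patient who dies before Day 56 cannot show recovery delayed beyond 56 days. So under 10.5.1, a related event that is fatal without an earlier Grade 4 record enters neither limb. The documents adopt CTCAE without printing its grade definitions, but the gap does not depend on the label Grade 5, since the rule never mentions death.

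**Step 2: what could the omission cost?**

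The documents state no stopping probability for the lead-in and no toxicity rate for the combination, so there is no figure to reproduce and the rates below are assumptions. Inputs from the plan: 10 patients, stop at 4 or more. Assumed:

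- p = chance that a patient has a related Grade 4 or fatal non-hematologic event;
- s = share of those patients whose event was fatal and never recorded as Grade 4.

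Patients are treated as independent, and only the non-hematologic limb is considered.

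P(stop) = 1 − Σ (k = 0 to 3) C(10,k) q^k (1−q)^(10−k), with q = p if fatal events count and q = p(1−s) as written.

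Example with p = 0.20 and s = 0.25:

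- fatal events counted, q = 0.20: 1 − (0.1074 + 0.2684 + 0.3020 + 0.2013) = 0.121;
- as written, q = 0.20 × 0.75 = 0.15: 1 − (0.1969 + 0.3474 + 0.2759 + 0.1298) = 0.050.

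| p | Fatal events counted | As written, s = 10% | s = 25% | s = 50% |
|---|---|---|---|---|
| 20% | 0.121 | 0.088 | 0.050 | 0.013 |
| 30% | 0.350 | 0.273 | 0.169 | 0.050 |
| 40% | 0.618 | 0.513 | 0.350 | 0.121 |

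**Step 3: causality.** The rule asks for *probably related to the combined treatment*. Section 11.1.6 offers YES or NO, and Section 11.1.5.1 gives related or unrelated as an example. No section defines *probably*, maps it to YES, or says who decides.

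**The case against.** Four points against the concern have weight.

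**Neutropenia.** Section 1.5 names pancytopenia as the most anticipated side effect and cites a median of 36 days to ANC ≥1000 with CPX-351. A patient who dies of toxicity during induction would probably have had Grade 4 neutropenia, and so may count under the synopsis and Sections 5 and 10.1. A reader might infer that four toxic deaths in ten would score zero under every version of the rule. The documents do not support that. It is possible only under 10.5.1 read alone, and only if none of the four events was ever recorded as Grade 4. What stands is that the other versions would count such a patient for neutropenia, not for the death.

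**Progression through Grade 4.** The rule counts patients who develop a Grade 4 event, and Section 11.3.2 requires a separate record when a persistent event worsens. Fatal sepsis or bleeding first recorded as Grade 4 could therefore count. This limits the gap to events with no Grade 4 record, and it is why s matters.

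**Rates.** It is tempting to quote the chance of four or more related deaths in ten at high death rates. No such rate appears in the documents; the 2% for CNS hemorrhage concerns a single cause. The chance is about 0.001 at a 5% death rate and 0.013 at 10%.

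**Causality and oversight.** A reader might infer that the required rating cannot be obtained at all. That goes too far: YES/NO is presented as a general guideline, related/unrelated as an example, the eCRF is not among the documents, and Appendix F uses another graded relatedness term. YES could reasonably be read to include *probably*, but this is not written. Deaths also reach the safety department as SAEs, and the sponsor or IRB may terminate the study (Section 3.3). Those routes are discretionary and do not replace a prespecified count.

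**Conclusion.** The omission is plain in the text: no statement of the rule counts a fatal event as toxicity, and 10.5.1 has no neutropenia limb that might capture the patient by another route.

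Its size is uncertain. With a quarter of events fatal and never recorded as Grade 4, the limb's chance of stopping falls by 0.071, 0.181 and 0.268 at total event rates of 20%, 30% and 40% (0.121 − 0.050, 0.350 − 0.169, 0.618 − 0.350). With a tenth, the falls are 0.033, 0.077 and 0.105. These figures rest on assumed p and s, independent patients, and 10.5.1 read literally. They do not estimate what would happen under the versions that include Grade 4 neutropenia.

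The causality mismatch is real, but it is a matter of reconciling wording and does not show that the rule is unusable.

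**What to change.** In the synopsis and Sections 5, 10.1 and 10.5.1, define the non-hematologic event as Grade 4 or Grade 5 (fatal), so that a related death counts whether or not a Grade 4 record came first. Grade and causality are already collected, so no new data are needed. The downside is that slightly more events may count toward the gate.

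Separately, reconcile *probably related to the combined treatment* with Sections 11.1.6 and 11.1.5.1: state which recorded category qualifies and who makes the determination. This should be a deliberate choice. Accepting a YES for either study drug, for example, could broaden a trigger now worded for the combination. The patient-count thresholds are a different question and are not addressed here.
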